Patients with diabetes mellitus are at higher risk of developing heart failure compared to those without diabetes. Furthermore we have shown previously that diabetics have reduced resident cardiac progenitor cell number and function, and that this can be improved *in vitro* and *in vivo* (in animal models) using a thiamine analogue. Although the thiamine analogue improved progenitor cell function in cell cultures from both diabetic and non-diabetic animals, the diabetic animals had worse function initially.

1.4 **Design and Outcomes**

This is a single centre, randomised, double-blind, controlled phase 2b trial, built on the infrastructure of an ongoing observational trial. Participants listed for inpatient urgent coronary artery bypass grafting (CABG) will be randomised to thiamine or placebo, for 3-5 days before their procedure. At the time of CABG, the right atrial appendage, which is discarded as a normal part of the procedure, will be collected as well as a small left ventricular biopsy (both of these techniques being a routine part of our current observational study).

The primary outcome is the proliferation ability of resident cardiac progenitor cells, as measured by BrdU activity.

Secondary outcomes are other functional measures, such as the ability to differentiate into cardiomyocytes, as measured by the number of GATA-4 and connexin-43 positive cells after exposure to differentiation medium, and measurement of the level of transketolase to determine the activation of pentose phosphate pathway.

Our primary hypothesis to be tested is that treatment with thiamine will improve the primary outcome in diabetics and non-diabetics. We also wish to test the hypotheses that treatment with thiamine will improve the secondary outcomes in diabetics and non-diabetics, and that diabetics receiving placebo have reduced resident cardiac progenitor cell number and function compared to non-diabetics receiving placebo.

1.5 ***Interventions and Duration***

Patients will be randomised to oral thiamine (2g/day) or matching placebo once listed for inpatient CABG. Total length of time on intervention treatment will be 3-5 days.

1.6 ***Sample Size and Population***

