The number of patients to be randomised in total is 40. Randomisation will be stratified based on diabetic status (non-diabetic/diabetic). The study population will be those patients admitted to hospital and awaiting urgent (i.e. inpatient) coronary artery bypass surgery, without valvular heart disease requiring intervention.

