The interventions (thiamine/placebo) will be bought by the Southern District Health Board Clinical Trials pharmacist from Pharmaceutical Compounding NZ Ltd, Auckland. The capsules will be packed into 20 capsule bottles by Pharmaceutical Compounding NZ Ltd (Licenced Pharmacy). Deliveries to the Southern District Health Board will be in batches of 15 bottles of active intervention and 15 bottles of placebo at a time. They will be stored in the Cardiology Research Nurses office in a designated locked area designed for dispensing of study medication. This room is kept at 21-22 degrees Celsius, which should be sufficient to supply the supplied 6 month shelf life for the study drugs.

5.3 **Randomisation procedure**

Prior to delivery of study drug to the Cardiology Research Nurses, the Clinical Trials Pharmacist will label the study drugs. This will be based on a randomisation list generated from <http://www.randomization.com>, where we will use 5 blocks of 4 participants each for the diabetic and nondiabetic arms of the trial. After labeling the study drugs, the Clinical Trials Pharmacist will hold both hard and soft copies of the randomisation lists, which will only be made available to the study investigators at the time of statistical analysis, i.e. unblinding.

5.4 **Concomitant Interventions**

None

5.5 **Adherence Assessment**

Study nurses will assess the participants prior to CABG to determine adherence with medication, by means of a pill count and patient questioning. In addition, functional B1 assays will be performed as described in the laboratory evaluations below.

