9.1.2 Secondary outcomes

Secondary outcomes are other functional measures, such as the ability to differentiate into cardiomyocytes, as measured by the number of GATA-4 and connexin-43 positive cells after exposure to differentiation medium, and measurement of the level of transketolase to determine the activation of pentose phosphate pathway

9.2 **Outcomes discussion**

Primary and secondary outcomes will be measured without knowledge of treatment assignment (i.e. blinded).

Bromodeoxyuridine (BrdU) is a thymidine analogue that is taken up by cells actively replicating DNA. As such it is widely used as an assay to determine proliferation of cells, and has appeared in over 20,000 biomedical science articles.¹⁹ In addition, we have demonstrated accuracy in our laboratory, with our animal studies demonstrating

a coefficient of variation of 9% in non-diabetic animals and 13-14% in diabetic animals. As such, it is a valid test to use to assess the function of resident CPCs.

9.3 **Sample Size and Accrual**

The primary outcome will initially be assessed in treated vs non-treated groups (combining diabetics with non-diabetics) and then stratified by diabetic status. We therefore calculated a sample size powered by subgroup (diabetic vs non-diabetic) status. Based on our previous data, with a sample size of 10 in each group (non-diabetic no active treatment, non-diabetic active treatment, diabetic no active treatment, diabetic active treatment) giving a total of 40 patients in total, we will have 99% power and 91% power, in non-diabetics and diabetics respectively, to detect a two-tailed 30% difference in primary outcome with treatment at a significance level of 0.05. Here we use a t-test to compare groups, with data coming from assessment of BrdU activity in CPCs isolated from treated and untreated animals.¹⁰ Note that we may have higher power, as we detected a 79% and 106% increase in mean proliferation activity of stem cells in treated non-diabetic and diabetic animals, respectively, compared with control. However given the uncertainty moving from an animal model to humans, we felt it prudent not to limit groups to less than 10 patients each.

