Accrual rate is expected to be approximately 1-2 participants per fortnight. This is based on current accrual rates of 2-4 participants per fortnight in the observational study – many of these will be eligible for inclusion in this trial and are likely to volunteer based on the low toxicity of the intervention. Given the exclusion of the highest risk cases (those with impaired left ventricular systolic function or those undergoing cardiac surgery on an emergency basis) and the short duration of treatment, we expect the vast majority of those enrolled to complete allocated treatment until CABG, i.e. a low loss to follow-up rate.

9.4 **Data Monitoring**

An interim blinded analysis of the toxicity data will be performed after recruitment of 20 patients by the study team. We expect there to be few adverse experiences on or off active treatment. If more than 20% of participants report adverse experiences, then a separate Data and Safety Monitoring Board will be recruited consisting of at least two clinicians independent of the investigators. These will be supplied with the toxicity data and the unblinding codes, if required. If, in their opinion, excess toxicity is seen with active treatment, a recommendation to halt the trial can be made to the study investigators.

An interim analysis of study recruitment will be made one year after randomisation of the first subject. If recruitment is less than 20 subjects, we will attempt to assess the cause of this slow recruitment. This will be done by comparing with recruitment to the observational study and analysis of screening logs. If study validity can be maintained, an amendment to the study will be made to rectify perceived causes of slow recruitment.

No interim analysis will be made for primary or secondary outcomes given the small number of study participants.

9.5 **Data Analyses**

A standard two-tailed t-test will be used to compare the primary outcome between treated and non-treated groups, using an intention-to-treat analysis. Separate analysis of the primary outcomes stratified by diabetic status will be performed using a t-test. For secondary analyses, differences across multiple groups will be assessed using an analysis of variance (ANOVA) test followed by a Šidák-Holm multiple comparison test. Comparison between two groups will be assessed using t-tests.

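### Section 9.5 does not say which rule tests thiamine against placebo on the secondary outcomes, does not limit Šidák-Holm to the stated contrasts, and plans no diabetes-adjusted thiamine effect

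*Protocol*

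**What the plan says.** Protocol section 9.5 gives two rules for the secondary analyses. First, "differences across multiple groups will be assessed using an analysis of variance (ANOVA) test followed by a Šidák-Holm multiple comparison test". Second, "Comparison between two groups will be assessed using t-tests". It gives neither the number of groups nor the list of comparisons.

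Section 1.4 states what is to be learned. One hypothesis is that "treatment with thiamine will improve the secondary outcomes in diabetics and non-diabetics". The other is that "diabetics receiving placebo have reduced resident cardiac progenitor cell number and function compared to non-diabetics receiving placebo". Together these make three contrasts: thiamine versus placebo in diabetics, the same in non-diabetics, and diabetic versus non-diabetic on placebo.

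The groups come from section 9.3, which plans "with a sample size of 10 in each group (non-diabetic no active treatment, non-diabetic active treatment, diabetic no active treatment, diabetic active treatment"), 40 patients in all. Section 1.6 says "Randomisation will be stratified based on diabetic status (non-diabetic/diabetic"), and section 5.3 carries this out: "we will use 5 blocks of 4 participants each for the diabetic and nondiabetic arms of the trial".

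The primary outcome has a clearer structure. Sections 9.3 and 9.5 compare treated with untreated patients overall and then within each diabetic stratum. Section 10.2 says that the investigators will unblind the combined database and carry out the analyses described.

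**The concern.** Thiamine versus placebo within diabetics is a comparison of two groups. It is also one pair within a multiple-group analysis. Both rules in section 9.5 fit it, and they set different bars. The choice would fall to the investigators, who hold the unblinded data when they analyse.

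Two losses of efficiency may follow:

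- **Multiple-group rule applied to every pair of cells.** Half of the correction goes to pairs that answer no stated hypothesis.
- **Two-group rule applied to all treated versus all untreated patients.** Any difference between diabetics and non-diabetics counts as noise, although it was a randomisation stratum. The protocol itself expects such a difference (sections 1.4 and 2.1).

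At stake is the chance of detecting an effect on differentiation and transketolase in a trial of 40 patients. The primary result is not affected.

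**Working it through.** **The plan's own figure.** The protocol gives no effect size, SD or power for any secondary outcome, so there is nothing to reproduce. The 99% and 91% in section 9.3 concern the primary outcome and do not bear on this point.

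**Inputs.** From the documents: four cells of 10 (section 9.3) and two-sided alpha 0.05 (stated in section 9.3 for the primary outcome, carried over here). Assumed: normal data, equal SD in all cells, and a thiamine effect of 1.0 SD in both strata (range 0.8 to 1.55 SD).

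**Step 1: count the pairs.** Four cells give 4 × 3 / 2 = 6 pairs. Three match section 1.4. The other three do not: diabetic versus non-diabetic with both on thiamine, and the two pairs that differ in both treatment and diabetes.

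**Step 2: the bar for one and the same pair.** The first-step Šidák level is 1 − 0.95^(1/m).

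- m = 6: 0.0085
- m = 3: 0.0170
- two-group t-test rule: 0.05

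**Step 3: power within a stratum at 1.0 SD.** The noncentrality is 1.0 × √(10/2) = 2.24. At the first step alone (pooled variance, 36 df), power is about 31% for m = 6 and 40% for m = 3. The later Holm steps add to this. Simulating 40,000 four-cell trials, with the strata differing by 0 or 1 SD, gives:

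| Assumed effect | Six pairs after ANOVA | Three stated contrasts |
|---|---|---|
| 0.8 SD | 19–22% | 27–30% |
| 1.0 SD | 34–37% | 43–48% |
| 1.55 SD | 80–81% | 86–89% |

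Separate runs at 1.0 SD differ by a point or two (33–37% against 43–46% in one). The gap is about 9–10 points in each. It narrows when the strata differ by more than 1 SD, because the step-down then relaxes sooner. An unadjusted two-group t-test (18 df) at 1.0 SD has 56%.

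**Step 4: overall thiamine effect, 20 versus 20, at 1.0 SD.** Adjusted for stratum, the noncentrality is 1.0 / √(2/20) = 3.16 with 37 df, so power is 87%. This does not depend on how far apart the strata are.

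For the unadjusted pooled t-test with strata g SD apart, the expected within-arm variance is v = (19 + 20 × (g/2)²) / 19. The difference must exceed about 2.024 × √(v/10), while its true standard error under stratified allocation stays √(1/10) = 0.316.

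| g | v | Threshold | (1.0 − threshold) / 0.316 | Approximate power | Simulated |
|---|---|---|---|---|---|
| 0 | 1.00 | 0.640 | 1.14 | 87% | 87% |
| 1 | 1.26 | 0.719 | 0.89 | 81% | 81% |
| 2 | 2.05 | 0.917 | 0.26 | 60% | 61% |

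Adjustment therefore gains 0, 6 or 26 points. At 0.8 SD the adjusted effect has 69% power, and the unadjusted test has 69% (g = 0) or 60% (g = 1). At 1.55 SD both exceed 99% for g of 0 or 1.

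**The case against.** The strongest defence is that section 9.5 already permits what is asked for. Its t-test sentence covers thiamine versus placebo, pooled or within a stratum. The word ANOVA does not exclude a two-factor model, and Šidák-Holm can be applied to any chosen set of contrasts. A list of contrasts and model terms for secondary outcomes often sits in the SAP, which is not shown.

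Much of this stands, and it rules out four stronger readings that a reader might infer:

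- **That thiamine's effect on the secondary outcomes is never estimated.** The t-test sentence allows it, and the pairs include it within each stratum. Only a diabetes-adjusted estimate is unspecified.
- **That all six pairs will be tested.** Four groups is a fair inference from section 9.3. All-pairs testing is a possible reading that the text does not state.
- **That type I error is inflated by the extra pairs.** Where Šidák-Holm is applied, family-wise error within each outcome is held. Extra pairs make the test more conservative.
- **That moving from six pairs to the stratified effect gains about 50 points (from 34–37% to 87%).** That sets a 10-versus-10 effect in one stratum against a 20-versus-20 overall effect. These are different estimands, and the second relies on similar effects in both strata.

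The defence does not settle which of the two rules applies. The protocol names specific methods, and section 10.2 makes them the analyses to be carried out. As written, they leave the same contrast open to a bar of about 0.0085 or 0.05.

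It can also be said that an overall thiamine effect is not one of the three contrasts in section 1.4. However, section 1.4 words the primary hypothesis in the same way, in both kinds of patient, and section 9.3 takes that to mean combined first and then by stratum. Giving the secondary outcomes the same order is consistent with the protocol.

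**Conclusion.** The point holds as a matter of clarity and efficiency in the secondary analyses. Section 9.5 leaves open which rule governs thiamine versus placebo, does not confine the correction to the stated contrasts, and does not use the randomisation stratum.

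The size depends on how the text is read. If all six pairs are compared, the three without a hypothesis cost about 9–10 points of within-stratum power at 1.0 SD. If a pooled unadjusted t-test is used, the loss against the stratified effect is nil when the strata do not differ, about 6 points at a 1 SD difference and about 26 points at 2 SD.

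These figures rest on assumed effect sizes, equal SDs and, for the overall effect, similar action in both strata. The only variability data in the protocol (section 9.2: BrdU in animals, coefficient of variation 9% in non-diabetic and 13–14% in diabetic animals) suggest that the SDs may not be equal. The direction of the finding does not depend on the exact values. Validity and the primary outcome are not at risk.

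**What to change.** Rewrite the secondary part of section 9.5, or settle it in the SAP, before unblinding:

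1. For each secondary outcome, estimate the thiamine effect in a model with treatment and diabetes stratum as randomised. Report the treatment-by-diabetes interaction as supportive.
2. Apply Šidák-Holm only to the three contrasts of section 1.4, and list them.
3. State that the two-group t-test sentence does not override items 1 and 2.

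The cost is one paragraph, with no new data and no change to sample size or conduct. The downside is that cross-cell pairs outside the three contrasts are not formally tested. They can still be described by cell means with confidence intervals.

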11 OTHER ISSUES

11.1 ***Health and Disability Ethics Committee Review and Informed Consent***

This protocol, the informed consent document, the patient information leaflet, and any subsequent modifications will be reviewed and approved by the Health and Disability Ethics Committee. A signed consent form will be obtained from the subject. The consent form will describe the purpose of the study, the procedures to be followed, and the risks and benefits of participation.

11.2 ***Subject Confidentiality***

All laboratory specimens, evaluation forms, reports, and other records (including images such as echocardiographic or angiographic images) that leave the care of the investigators will be identified only by the Study Identification Number (SID) to maintain subject confidentiality. All records will be kept in a file protected by a locked door. Clinical information will not be released without written permission of the subject, except as necessary for monitoring by the Southern District Health Board, the Health and Disability Ethics Committee, the sponsor, or the sponsor's designee.

11.3 ***Study Modification/Discontinuation***

The study may be modified or discontinued at any time by the Health and Disability Ethics Committee, the sponsor, Southern District Health Board, or the investigators, as part of their duties to ensure that research subjects are protected.

12 PUBLICATION OF RESEARCH FINDINGS

Scientific publication of results will be organised and determined by the study investigators. In particular, there will be no role of the study funder or sponsors in the analysis of results, or in writing or submission of manuscripts. A lay summary will be provided to participants and funding organisations along with a copy of scientific publication generated.

Appendix

A1. Letter of support for left ventricular biopsy

18 November 2012

To whom it may concern,

The method to obtain a tiny (1.5 x 1.5 x 10 mm) left ventricular epicardial biopsy during cardiac surgery as proposed by [name] et al. in the amendment to their Human Ethics application (LRS/12/01/001) is a recognised technique for obtaining myocardial tissue. Inherently to take a biopsy, it will carry a degree of risk, however, for the proposed procedure it is expected to be minimal. To my knowledge, no side effects have been reported with this procedure in the medical literature. The biopsy will be done intra-operatively under direct vision and unlikely to result in any adverse event. In my opinion, this is a very low risk procedure. Therefore I support the approval of this study as it is likely to contribute significantly to the advancement of medical knowledge in the field that this research group is working on and the risk of biopsy is minimal.

Sincerely,

[name], PhD, FRACS
Professor, University of Melbourne,
Consultant Cardiac Surgeon, Royal Children's Hospital, [name]
[contact]; [contact]; [contact].
E-mail: [contact], [contact]

A2. Scientific statement on LV epicardial biopsy – for amendment to project LRS-12-01/001

[name], [name], [name], [name], [name], [name], [name]
21th September 2012

A2.1. Introduction

This brief statement examines the use of epicardial left ventricular biopsies in the context of the project entitled “Effect of catecholamines on functions and signaling in obese human diabetics (LRS-12-01/001)”. Full details regarding the project, including background, hypotheses, and protocol can be found in the other documents accompanying the request for approval of amendment to the project.

A2.2. How is an epicardial left ventricular biopsy obtained?

In patients undergoing coronary artery bypass grafting (CABG) who have consented to having an epicardial biopsy, cardiopulmonary bypass (CPB) will be instituted using standard anticoagulation protocol and cannulation. An area of the anterior wall of the left ventricle (LV), free from any epicardial scarring following previous myocardial infarction, will be identified. A wedge (1.5 x 1.5 x 10 mm) will be biopsied. The site will be repaired using a single pledgeted or non-pledgeted 4-0 prolene suture. In total, the additional operating time is expected to be approximately one or two minutes.

A2.3. What is the indication for epicardial left ventricular biopsy?

Diabetes is associated with a significantly increased risk of heart failure, both with impaired and preserved ejection fraction. One of the primary goals is to further characterise diabetic heart disease. To this point, we have used atrial tissue removed routinely during surgery. Our atrial tissue findings to date with regard to calcium handling in the hearts with preserved ejection fraction have been unexpected. However, calcium handling in atrial and ventricular myocytes is known to be different in animal studies (see, for example references [1, 2]). As clinical heart failure is due predominantly to disease in the ventricle, analysis of ventricular tissue is clearly required.

Another technique for obtaining ventricular myocytes is via a percutaneous endomyocardial approach. However independent advice from interventional cardiologists in Dunedin and Auckland recommended considering an epicardial biopsy at the time of CABG as the safest approach.

A2.4. What are the risks of epicardial left ventricular biopsy?

Obtaining left ventricular epicardial biopsies is an internationally established technique with no reported adverse effects. On the other hand, many cardiac surgeons (including in Dunedin) undertake decompression of the left ventricle routinely during valve procedures, which by necessity requires a transmural ventriculotomy. The proposed epicardial biopsy taken

under direct vision is a less invasive procedure with a similar technique both for obtaining the biopsy and subsequent repair, meaning that there should not be any significant learning curve for the procedure.

A number of international centres have obtained left ventricular epicardial biopsies and reported their results. A study from 1992 included six patients, and noted that there were no complications [3]. A 1995 study using epicardial biopsies did not give the number of biopsies taken for their study, but reported that the procedure had been found to be safe in over 40 procedures [4]. A 2005 study included 26 patients, and did not report any complications [5]. A 2010 study from the same group in Burlington, Vermont included a further 21 patients, and again did not note any complications [6]. Most recently a group from Oxford performed both atrial and epicardial ventricular biopsies, without note of any complications [7]. So, to the best of our knowledge, no complication has ever been reported for this procedure.

